5.5.4 Instructions for prescribing and taking study treatment

The investigator must promote compliance by instructing the patient to take the study treatment exactly as prescribed and by stating that compliance is necessary for the patient's safety and the validity of the study. The patient must also be instructed to contact the investigator if he/she is unable for any reason to take the study treatment as prescribed.

Patients will be provided with medication as described in Section 5.1.

All kits of study treatment assigned by the IRT will be recorded / databased in the IRT. All used and unused study medication/packaging must be returned by the patient at each study visit and/or at the time of discontinuation. If any faults are identified with either the device and/or the blisters, these should be returned to Novartis Drug Supply Management with the completed Device Return Form. The forms will be supplied to each investigator site by the Field Monitor.

All dosages prescribed and dispensed to the patient and all dose changes during the study must be recorded on the Dosage Administration Record eCRF page.

At Visit 1 all patients will be instructed how to use an MDI to administer rescue salbutamol/albuterol correctly. At Visit 101 patients will be trained to the use of the eDiary, peak flow meter and Accuhaler (Appendix 3). At Visit 102 all patients will be fully trained in the correct use of the Concept1 and Twisthaler inhaler devices used to administer study medication. Patients who are unable to use either device correctly at Visit 102 will not be eligible to enter the treatment epoch. Additional training devices will be supplied for demonstration purposes. At clinic visits the investigator should check the patient's use of the inhalational devices to ensure correct use of each device. If required, further device training should be provided. Patients will be instructed to contact the site if the device is not functioning properly.

Patients will be instructed to take their dose of study medication at approximately the same time every evening regardless of their time of sleep, meal or other activities. Patients will be instructed to rinse their mouth 2 times with approximately 30 mL of water after the last inhalation of the study drug following sequential inhalations from devices. Water used for mouth rinsing should NOT be swallowed.

The study drugs must be taken in the evening (between 5:00 and 8:00 pm), and consist of sequential single inhalations from the following devices:

- One inhalation from the Concept1 device containing either QMF149 or placebo
- One inhalation from the Twisthaler[®] device containing either MF or placebo

The 2 inhalations should be taken as close together in time as possible. Instructions for use of the Concept1 inhaler and Twisthaler® are provided in Appendix 1 and Appendix 2.

5.5.5 Permitted dose adjustments and interruptions of study treatment

The Study drug dose adjustments and/or interruptions are not permitted unless the investigator considers an interruption is necessary for the treatment of an adverse event. Any interruption of study medication should be for the shortest time period possible and recorded in the Dosage Administration Record eCRF.

In case of blind broken, the study medication is to be permanently discontinued.

5.5.6 Rescue medication

At Visit 1, all patients will be provided with a SABA (100 microgram salbutamol or 90 microgram albuterol via MDI) which they will be instructed to use throughout the study as rescue medication. Nebulized salbutamol/albuterol is not allowed as rescue medication throughout the entire trial. No other rescue treatment is permitted and use of spacer for rescue medication is not allowed at any time throughout the study.

In order to standardize measurements, patients will be instructed to abstain from taking rescue medication (salbutamol/albuterol) within 6 hours of the start of each visit where spirometry is being performed unless absolutely necessary. If rescue medication is taken within 6 hours prior to spirometry assessments, then the visit should be rescheduled to the next day if possible.

Bronchodilator medications that the patients used prior to Visit 1 must be recorded in the asthma-related prior/concurrent medication page of the eCRF, with the stop date for these bronchodilators recorded as the date of Visit 1. The rescue salbutamol/albuterol provided at Visit 1 for use during the study should NOT be recorded on the asthma-related prior/concurrent medication page of the eCRF. From Visit 101, patient should be instructed to record daily use of rescue medication (number of puffs taken in the previous 12 hours) each morning and evening throughout the 12 week treatment epoch in her/his electronic diary.

The rescue salbutamol/albuterol will be provided to the patients by the study center and reimbursed locally by Novartis or supplied to the investigator sites locally by Novartis.

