4.1 Inclusion criteria

Patients eligible for inclusion in this study must fulfill all of the following criteria:

- 1. Written informed consent must be obtained from all patients before any study-related assessment is performed. Patients below the legal age of consent are required to have the Parental Informed Consent signed by the patient's parent/legal guardian; adolescents are required to sign the Assent Form.
- 2. Male and female adolescents aged ≥ 12 to < 18 years old (depending upon regulatory and/or institutional Review Board (IRB)/Independent Ethics Committee (IEC)/REB approval and/or country participation) and male and female adults aged ≥ 18 years and ≤ 75 years old.
- 3. Patients with a documented diagnosis of asthma for a period of at least 3 months prior to Screening (Visit 1).
- 4. Patients who have used low dose ICS (Appendix 9), with or without another controller therapy (i.e., LABA, Leukotriene Receptor Antagonist (LTRA)) at stable dose for at least 1 month prior to Screening (Visit 1).
- 5. Adult patients must be symptomatic despite treatment with existing therapy. Patients must have ACQ-7 score ≥ 1.5 at Visit 101 and at Visit 102 (i.e., inadequately controlled).
- 6. Adolescent patients:
 - If taking low dose ICS (without LABA), patients must be symptomatic despite treatment with low doses of ICS. These patients must have ACQ-7 score \geq 1.5 at Visit 101 and at Visit 102 (i.e., inadequately controlled).
 - If taking low dose ICS / LABA, patients may be included only if ACQ-7 score ≥ 1 and <1.5 at Visit 101 (i.e., adequately controlled). However, ACQ-7 score must be ≥ 1.5 at Visit 102, directly prior to randomization.
- 7. Pre-bronchodilator $FEV_1 \ge 60\%$ and < 90% of the predicted normal value for the patient according to ATS/ERS criteria after withholding bronchodilators at both Visits 101 and 102.
 - Withholding period of bronchodilators prior to spirometry: SABA for ≥ 6 hours and FDC or free combinations of ICS/LABA* for ≥ 48 hours (14 days for once daily combinations, i.e., indacaterol), short acting anticholinergies (SAMA) for ≥ 8 hours, xanthines ≥ 7 days.

*In case of combination ICS/LABA, ICS should be continued.

Washout period of each drug should be kept as close as possible as above and should not be longer. If washout period is considered to be longer, please contact your Novartis Medical Monitor.

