5.5.8 Prohibited medication

Prohibited medications, as listed in Table 5-1, must not be taken during the study (unless for the treatment of asthma exacerbations). The specified minimum washout periods prior to Runin (Visit 101) and/or Randomization (Visit 201) are described in Table 5-1. The classes of medication listed in Table 5-2 are not permitted to be taken during the study. The medications in Table 5-3 are only permitted under the circumstances given. Each concomitant drug must be individually assessed against all exclusion criteria and the tables below to see if it is allowed. If in doubt, the investigator should contact the medical monitor before randomizing a patient or allowing a new medication to be started.

If a patient takes systemic corticosteroids within 7 days prior to a study visit, the visit must be rescheduled to allow a washout of 7 days.

Page 38

Table 5-1 **Prohibited Asthma-Related Medications**

lable 5-1 Pronibited Asthma-Relate	ed Medications
Class of medication	Minimum washout period prior to Run-in (V101) 1, 2, 3, 4
Short acting anticholinergics (SAMA)	Must be discontinued 8 hours prior to Visit 101
Fixed combinations of β_2 -agonists and inhaled corticosteroids	Must be discontinued 48 hours prior to Visit 101; Patients should continue with an ICS until Visit 101 when patients will be switched to fluticasone propionate 100 µg b.i.d. (or equivalent dose) for Runin; the last dose of Run-in medication will be taken in the morning of visit 102
Inhaled corticosteroids ¹	All patients must be treated for asthma with fluticasone propionate 100 microgram b.i.d. (or equivalent dose) from Visit 101 to Visit 102 (Figure 3-1); all other ICS must be discontinued at Visit 101
Fixed combinations of short-acting β_2 -agonist and short-acting anticholinergic	Must be discontinued 8 hours prior to Visit 101
Leukotriene Receptor Antagonist (LTRA) and leukotriene synthesis inhibitors	Must be discontinued 7 days prior to Run-in (Visit 101)
Long-acting β ₂ -agonists (LABAs)	LABAs b.i.d. must be discontinued 48 hours prior to Visit 101. LABAs o.d. (i.e., indacaterol) must be discontinued at Visit 1 (14 days prior to Visit 101). All patients will be provided with SABA at Visit 1 for use throughout the study
Salbutamol/albuterol (SABA) provided at Visit 1 and throughout study as required for rescue medication	Must be withheld 6 hours prior to Visit 101 and Randomization (Visit 201) ⁴

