#### **2.4.2 Prior, concomitant and post therapies**

Each medication, either an asthma or non-asthma medication, will have the start and end dates recorded on the eCRF. Separate tables will be provided for medications which were started and stopped prior to the first dose of study treatment and medications which were taken concomitantly to the study treatment (regardless of whether continued or started after the first dose of study treatment).

Asthma medications will be summarized by the route of administration, the recorded prespecified drug subcategories (including types of combination) and the coded preferred terms. The summary will be repeated by showing ingredients instead of preferred terms. Non-asthma medications will be summarized by route of administration and preferred term.

Surgical and medical procedures (non-drug therapies) will be coded using MedDRA and presentations will be done by MedDRA primary system organ class and preferred term, separately for prior procedures and those after start of study treatment.

Short acting beta2 agonist (SABA) rescue medication usage (mean number of puffs) during the screening epoch will be summarized.

Patients taking prohibited concomitant medications will be noted in the summary of protocol deviations.

All summarizations will be by treatment group in the Safety Set.

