OTH12A	Compliance failure of the patient influencing the safety and efficacy data as per investigator judgement
OTH14A	Patient receiving investigational drug other than study drug during the course of the study
COMD02A	SAMA taken less than 8 hours prior to visit 101
COMD03A	Fixed combinations of $\beta$ 2-agonists and inhaled corticosteroids taken within 48 hours prior to Visit 101

Deviation ID	Description of Deviation
COMD04A	Fixed combinations of short-acting $\beta$ 2-agonist and short-acting anticholinergic taken within 8 hours prior to Visit 101
COMD05A	Leukotriene Receptor Antagonist (LTRA) and leukotriene synthesis inhibitors taken within 7 days prior to Run-in (Visit 101)
COMD06A	LABA b.i.d taken within 48 hours prior to visit 101
COMD07A	LABA o.d continuing at visit 1
COMD08A	Short Acting B2 Agonist, other than rescue medication is continuing after visit 1
WTH01A	Patient still on study treatment even after having 1 severe asthma exacerbation requiring treatment with systemic corticosteroids or hospitalizations
WTH06A	Blind broken and study treatment not permanently discontinued
COMD16A	Banned asthma related concomitant Medications used during the study*
Deviations leading to exclusion of data collected after occurrence of that event, from all analyses set	
WTH07A	Study procedures performed after withdrawing of informed consent

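### Protocol 5.5.6 fixes the eCRF stop date of prior bronchodilators at Visit 1, although Table 5-1 lets several continue after it, so washout cannot be read from that record

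*Protocol*

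**What the plan says.** Protocol 5.5.6 (Rescue medication) states: "Bronchodilator medications that the patients used prior to Visit 1 must be recorded in the asthma-related prior/concurrent medication page of the eCRF". It does not restrict the class. The entry is to be made "with the stop date for these bronchodilators recorded as the date of Visit 1". The next sentence keeps the study-supplied salbutamol/albuterol off the same page.

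Table 5-1 in section 5.5.8 sets the last permitted use of several bronchodilators relative to Visit 101:

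- b.i.d. LABA: "LABAs b.i.d. must be discontinued 48 hours prior to Visit 101".
- Fixed combinations of a beta-2 agonist with an ICS: "Must be discontinued 48 hours prior to Visit 101; Patients should continue with an ICS until Visit 101".
- SAMA, and fixed SABA/SAMA combinations: "Must be discontinued 8 hours prior to Visit 101".
- Xanthines: 7 days before Visit 101.

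For two classes the table does name Visit 1 as the stopping point: o.d. LABA, and SABAs other than the study supply.

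Inclusion criterion 7 gives the same periods for ICS/LABA, SAMA and xanthines, and adds: "Washout period of each drug should be kept as close as possible as above and should not be longer". Section 3.1 allows at most two weeks between Visit 1 and Visit 101, and permits less.

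SAP 2.4.2 says that each medication "will have the start and end dates recorded on the eCRF". SAP 6.7 lists washout breaches that exclude a patient from the per-protocol set (PPS). COMD06A, for example, is "LABA b.i.d taken within 48 hours prior to visit 101". COMD02A, 03A, 04A and 12A do the same for SAMA, ICS/beta-2-agonist combinations, SABA/SAMA combinations and xanthines.

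**The concern.** Two instructions to the site collide. One sets how long a drug may be taken. The other sets what stop date is written down, whatever the patient did. Where the first allows use beyond Visit 1, the second yields a wrong entry even at a fully compliant site.

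The affected field bears on the washout before Visit 101. The FEV1 values before and after salbutamol at that visit decide eligibility and are covariates in the primary model. The PPS is meant to leave out patients who broke the washout. A prescribed stop date carries no information on whether they did.

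**Working it through.** The plan states no figure on this point, so there is nothing to reproduce. The check compares the recording rule with each washout period.

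**Inputs.** Interval between Visit 1 and Visit 101, G: at most 14 days = 336 h (section 3.1; Table 6-1 places Visit 1 at Day -35 to -21 and Visit 101 at Day -21). Required washout, W: 8 h, 48 h, 7 days = 168 h, or 14 days = 336 h for o.d. LABA (Table 5-1, criterion 7).

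**Formulas.**

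- Washout shown on the eCRF page = Visit 101 minus the recorded stop = G, whatever the true last dose.
- Longest use after Visit 1 that still meets the washout = max(0, G - W). This is also the largest error in the recorded date for a compliant patient.

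**Results.**

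| Class | W | G = 3 days (72 h) | G = 7 days (168 h) | G = 14 days (336 h) |
|---|---|---|---|---|
| SAMA, SABA/SAMA | 8 h | 72 - 8 = 64 h | 168 - 8 = 160 h | 336 - 8 = 328 h (almost 14 days) |
| b.i.d. LABA, ICS/LABA | 48 h | 72 - 48 = 24 h | 168 - 48 = 120 h | 336 - 48 = 288 h (12 days) |
| Xanthines | 168 h | 0 h | 0 h | 336 - 168 = 168 h (7 days) |
| o.d. LABA | 336 h | 0 h | 0 h | 0 h |

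**Effect on the deviation codes.** A code with threshold W, applied to the recorded date, flags a patient only when G < W. The true last dose does not enter. With a 14-day screening, a b.i.d. LABA taken on the morning of Visit 101 would show 336 h of washout against the 48 h required, and COMD06A would not flag it. The same holds for COMD02A, 03A, 04A and 12A once G reaches their W. Result: on this field the codes depend on the visit dates, not on drug intake.

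**Where the rule is right.** For o.d. LABA and for SABAs other than the study supply, Visit 1 is the required stopping point. For a compliant patient the recorded date is then correct.

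**Reach into the analysis.** The primary model is fitted on the full analysis set (FAS). SAP 2.5.3 sets trough values to missing for systemic corticosteroid use, rescue use or timing, not for LABA use. No stop date enters the model. The PPS is used only for a supportive analysis (SAP 2.2).

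**The case against.** The sentence stands under a heading on rescue medication, and the one after it deals with study-supplied SABA. It may have been meant only to close out the patient's previous reliever when the study inhaler is issued, and for that purpose Visit 1 is correct. This is plausible, but the text says bronchodilators in general, so a site cannot know. If only SABAs were meant, the wording still needs correcting.

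Section 3.1 has prohibited asthma medications replaced at Visit 1, and Table 5-1 calls its periods minimum washouts, so stopping everything at Visit 1 could satisfy the table. But criterion 7 says the washout should not be longer than listed, and Table 5-1 gives hour-based stops before Visit 101. These sections have to be reconciled; they do not settle which date to enter.

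The 12-day figure needs a full 14-day screening in a patient who needs only 48 h. That stands: it is a worst case, and section 3.1 allows a shorter screening where washout is short.

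Failures can surface elsewhere. Section 5.5.7 requires medications taken after enrolment to be recorded, medication is reviewed at each visit, and section 8.1 requires full verification of eligibility. Nor does the SAP say that the COMD codes are derived from this field. SAP 2.4.2 mentions dates only, which cannot resolve an 8 h or 48 h limit, and COMD08A presupposes that continuation after Visit 1 can be seen. All this stands, and it limits the point to this one record. It does not remove it: for a drug continued past Visit 1, sections 5.5.6 and 5.5.7 conflict, and nothing says which governs.

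A reader might also infer that LABA use in the MF arm is concealed and that the primary estimate is pulled toward zero. The documents do not support this. Any dilution would come from taking the drug, not from how an earlier stop date is recorded, and correct dates would leave the FAS estimate as it is. Use during the study has its own code (COMD16A). A washout failure at Visit 101 precedes randomization and cannot systematically favour an arm.

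**Conclusion.** The contradiction is real and the text is wrong as written, with limited consequences. Read as it stands, section 5.5.6 gives a false stop date for bronchodilators that Table 5-1 and criterion 7 let the patient take after Visit 1. In a compliant patient with a 14-day screening the error is up to 12 days for b.i.d. LABA or ICS/LABA, 7 days for xanthines and 328 h for SAMA. It shrinks with a shorter screening and reaches zero once the interval is no longer than the washout.

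Five PPS deviation codes cannot be reliably derived from the field. Washout failures are masked on that page, but not necessarily lost to the trial. The primary FAS result does not change. The documents do not say how many patients used the affected classes or how long screening usually lasted, so the effect on PPS membership cannot be sized.

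The conclusion assumes that the sentence covers all bronchodilators, as worded. If it was meant for SABAs only, what remains is an unclear instruction.

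**What to change.** Reconcile section 5.5.6 with Table 5-1 and inclusion criterion 7 in one of two ways:

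- have sites record the actual date of last use of each prior bronchodilator, with clock time where the washout is counted in hours; or
- limit the Visit 1 stop-date rule explicitly to the drugs that must stop at Visit 1, and record actual last use for the rest.

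State in the SAP that COMD02A, 03A, 04A, 06A and 12A are derived from actual last use.

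The cost is a one-sentence protocol correction, an eCRF completion note (with a time entry for the hour-based washouts) and a line in the SAP. No visit, procedure or washout period changes. A few more deviations may be counted.

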5.5.7 Concomitant medication

The investigator must instruct the patient to notify the study site about any new medications he/she takes after the patient was enrolled into the study. All medications, procedures and significant non-drug therapies (including physical therapy and blood transfusions) administered after the patient was enrolled into the study must be recorded in the concomitant medications/significant non-drug therapies eCRF.

Each concomitant drug must be individually assessed against all exclusion criteria/prohibited medication. If in doubt the investigator should contact the Novartis medical monitor before randomizing a patient or allowing a new medication to be started.

5.5.8 Prohibited medication

Prohibited medications, as listed in Table 5-1, must not be taken during the study (unless for the treatment of asthma exacerbations). The specified minimum washout periods prior to Runin (Visit 101) and/or Randomization (Visit 201) are described in Table 5-1. The classes of medication listed in Table 5-2 are not permitted to be taken during the study. The medications in Table 5-3 are only permitted under the circumstances given. Each concomitant drug must be individually assessed against all exclusion criteria and the tables below to see if it is allowed. If in doubt, the investigator should contact the medical monitor before randomizing a patient or allowing a new medication to be started.

If a patient takes systemic corticosteroids within 7 days prior to a study visit, the visit must be rescheduled to allow a washout of 7 days.

Page 38

Table 5-1 **Prohibited Asthma-Related Medications**

lable 5-1 Pronibited Asthma-Relate	ed Medications
Class of medication	Minimum washout period prior to Run-in (V101) 1, 2, 3, 4
Short acting anticholinergics (SAMA)	Must be discontinued 8 hours prior to Visit 101
Fixed combinations of β_2 -agonists and inhaled corticosteroids	Must be discontinued 48 hours prior to Visit 101; Patients should continue with an ICS until Visit 101 when patients will be switched to fluticasone propionate 100 µg b.i.d. (or equivalent dose) for Runin; the last dose of Run-in medication will be taken in the morning of visit 102
Inhaled corticosteroids ¹	All patients must be treated for asthma with fluticasone propionate 100 microgram b.i.d. (or equivalent dose) from Visit 101 to Visit 102 (Figure 3-1); all other ICS must be discontinued at Visit 101
Fixed combinations of short-acting β_2 -agonist and short-acting anticholinergic	Must be discontinued 8 hours prior to Visit 101
Leukotriene Receptor Antagonist (LTRA) and leukotriene synthesis inhibitors	Must be discontinued 7 days prior to Run-in (Visit 101)
Long-acting β ₂ -agonists (LABAs)	LABAs b.i.d. must be discontinued 48 hours prior to Visit 101. LABAs o.d. (i.e., indacaterol) must be discontinued at Visit 1 (14 days prior to Visit 101). All patients will be provided with SABA at Visit 1 for use throughout the study
Salbutamol/albuterol (SABA) provided at Visit 1 and throughout study as required for rescue medication	Must be withheld 6 hours prior to Visit 101 and Randomization (Visit 201) ⁴
Short acting β_2 -agonists (SABAs) (other than Salbutamol/albuterol provided at Visit 1 for rescue medication)	Must be discontinued at Visit 1 and are not permitted during the study
Parenteral or oral corticosteroids (systemic corticosteroids are permitted for the treatment of asthma exacerbations)	Must be discontinued 4 weeks prior to Run-in (Visit 101)
Intra-muscular depot corticosteroids	Must be discontinued 3 months prior to Run-in (Visit 101)
Monoclonal Antibody: IgE inhibitors and other asthma-related biologics (i.e., omalizumab), IL-5 inhibitors (e.g., mepolizumab)	Must be discontinued 4 months prior to Run-in (Visit 101)
Xanthines	Must be discontinued 7 days prior to Run-in (Visit 101)
Systemic mast cell stabilizers (e.g., cromoglycate, nedocromil, ketotifen)	Must be discontinued 7 days prior to Run-in (Visit 101)

¹ ICS must be discontinued at Visit 101. Treatment for recorded asthma exacerbation as defined in Section 6.4.9 is allowed ONLY until the asthma exacerbation is resolved (minimum wash-out of 7 days is required before scheduling a visit including spirometry assessment).

² This table is not considered all-inclusive. Medications should be assessed for adherence to the indication and other inclusion/exclusion criteria.

Table 5-2 Prohibited Medications

Class of medication	Minimum cessation period prior to Run-in (Visit 101)
Non-potassium sparing diuretics (unless administered as a fixed-dose combination with a potassium conserving drug	7 days
Non-selective systemic β-blocking agents	7 days
Cardiac anti-arrhythmics Class Ia	7 days
Cardiac anti-arrhythmics Class III	7 days, amiodarone 3 months
Other drugs with potential to significantly prolong the QT interval	14 days or 5 half-lives, whichever is longer
Strong inhibitors of cytochrome P4503A (e.g., ketoconazole)	7 days
Tricyclic antidepressants (tetracyclics which are similar in class with regards to drug interaction are also to be excluded)	14 days
Other investigational drugs	30 days or 5 half-lives, whichever is longer
Noradrenaline reuptake inhibitors	7 days
Live attenuated vaccine	30 days

Table 5-3 Medications Allowed Under Certain Conditions

iddic 0-0 Micalcations Anonca on	aci ocitalii ooliaitiolis
Class of medication	Condition
Mucolytic agents not containing bronchodilators	If stabilized for at least 4 weeks prior to Visit 1 and throughout the trial
Pure Selective Serotonin Reuptake Inhibitors (they must have no documented effect on any other neurotransmitters or other biological pathways, e.g., muscarinic pathway)	Treatment regimen is stable for at least one month at Visit 1
Inactivated influenza vaccination, pneumococcal vaccination or any other inactivated vaccine	Not administered within 48 hours prior to a study visit
Intra-nasal corticosteroids	Stable dose for at least 4 weeks prior to Visit 101; In the case of as needed, providing an established pattern of use has been documented
Antihistamines (e.g., loratadine, cetirizine)	If stabilized for at least 4 weeks prior to Visit 1 and throughout the trial; in the case of as needed, providing an established pattern of use has been documented
Topical corticosteroids for the treatment of eczema	In recommended doses and dosage regimens

³ These medications are also prohibited if administered for other indications.

⁴ SABA (salbutamol/albuterol rescue medication) should be withheld for at least 6 hours prior to spirometry measurements at clinic visits if possible. Clinic visits may be rescheduled if rescue medication were taken less than 6 hours prior to the spirometry assessments.

Class of medication	Condition
Maintenance immunotherapy for allergies	Stable dose for at least 3 months prior to Visit 101
	and unchanged throughout study treatment

Page 40

If indicated for the treatment of an asthma exacerbation, any treatment deemed necessary for the safety of the patient is allowed from the start of the asthma exacerbation event (Section 6.4.9) until the asthma exacerbation event is resolved.

5.5.9 **Emergency breaking of assigned treatment code**

Emergency treatment code breaks should only be undertaken when it is essential to treat the patient safely and efficaciously. Most often, study treatment discontinuation (TD) and knowledge of the possible treatment assignments are sufficient to treat a study patient who presents with an emergency condition. Emergency treatment code breaks are performed using the IRT. When the investigator contacts the system to break a treatment code for a patient, he/she must provide the requested patient identifying information and confirm the necessity to break the treatment code for the patient. The investigator will then receive details of the investigational drug treatment for the specified patient and a fax or email confirming this information. The system will automatically inform the Novartis monitor for the site and the Novartis Clinical Trial Head that the code has been broken.

It is the investigator's responsibility to ensure that there is a dependable procedure in place to allow access to the IRT/code break cards at any time in case of emergency. The investigator will provide:

- protocol number
- study drug name (if available)
- patient number

In addition, oral and written information to the patient must be provided on how to contact his/her backup in cases of emergency, or when he/she is unavailable, to ensure that unblinding can be performed at any time.

Study drugs must be discontinued after emergency unblinding. Study drugs must also be discontinued for any patient whose treatment code has been inadvertently broken.

